8.2.1 Primary Efficacy Analysis

The primary efficacy endpoints are the change from Baseline (CFB) in ADAS-cog score and the change from Baseline in ADCS-ADL score at Week 104 (Visit 13).

A delayed start design will be used to support the potential disease modifying effect of MK-8931 by comparing the 40mg/40mg arm to the Pbo/40mg arm. However, due to increased variance and anticipated dropout rate over time, the study is not powered to demonstrate significance on these endpoints, even if significance was demonstrated at 18 months.

All available data from the initial 78-week trial will be utilized in the analyses, even that from subjects who do not continue into long term safety trial. It is possible that the 40 mg dose may be dropped for reasons due to safety, in which case all subjects would receive 12 mg. The primary comparison in this case would be between the 12 mg / 12 mg arm and the Pbo / 12 mg arm (with any subjects receiving 40 mg or 60 mg excluded from the analysis).

The primary analysis approach will be conducted separately on each of the endpoints.

A longitudinal ANCOVA model will be used on the change scores, with time treated as a categorical variable so as not to impose any restriction on the trajectory of the means over time. The analysis model will adjust for the categorical factors of geographic region (US/Canada, Europe/Australia/New Zealand, Japan, Rest of the World), treatment (one or two remaining dose[s] of MK-8931 or placebo), gender, APOE genotype (APOE 4 positive, APOE 4 negative), baseline use of Vitamin E (0-400 IU/day, > 400 IU/day), baseline AD medication (use of AChEI or memantine, no use of AChEI or memantine), study cohort from the initial 78-week trial (Safety Cohort, Main Cohort) and the interaction of time-by-treatment, with the baseline values of MMSE and age included as continuous covariates. The baseline value of the dependent variable, as well as the baseline-by-time interaction term will also be included. The Week-78 change-from-Baseline mean treatment differences (MK-8931 – placebo), corresponding confidence intervals (CIs), and P-values will be estimated from this model. An unstructured covariance matrix will be used to model the correlation among repeated measurements.

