Three supportive analyses will be conducted on each of the Coprimary Endpoints. These analyses will be conducted to assess the effect of 1) missing data using a pattern-mixture model (“tipping-point” analysis), 2) the use of off-regimen data after the subject has permanently discontinued trial medication or after the subject has initiated AChEIs and 3) analyzing the data using the cLDA model on the MFAS population.

For the first sensitivity analyses (tipping-point), the model-based estimates of the mean treatment difference on the change scores, along with the corresponding confidence intervals and p-values will be provided for a range of c values which have been subtracted from the values imputed for the active arms (see 8.2.10) for more details). Of specific interest is the smallest c value that, for a given endpoint, transforms a statistically significant result to a non-statistically significant result.

For the second sensitivity analysis (excluding observations obtained after study medication discontinuation or after the initiation of AChEIs, memantine, or Vitamin E), the model-based estimates of the mean treatment difference on the change scores, along with the corresponding confidence intervals and p-values will be provided.

For the third sensitivity analysis (cLDA model on the MFAS population), the analysis of the primary efficacy endpoints will be conducted using a constrained longitudinal data analysis (cLDA) method proposed by Liang and Zeger [11]. This model assumes a common mean across treatment groups at baseline and a different mean for each treatment at each of the post-baseline time points. The response vector consists of baseline and the values observed at each post-baseline time point. Additional details pertaining to the cLDA model are included in Section 12.5. The model-based estimates of the mean treatment difference on the change scores, along with the corresponding confidence intervals and p-values will be provided as obtained using the cLDA model, with all of the same covariates that were included in the primary model (now excluding the terms for baseline and baseline-by-time interaction). An unstructured covariance model will be used.

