Although the baseline measurement is included in the response vector, it is independent of treatment. Hence, the Baseline means are constrained to be the same for different treatment groups. Note that in the event that there are no missing data, the estimated treatment difference from the above cLDA model will be identical to that from a traditional longitudinal analysis of covariance (ANCOVA) model that uses the Baseline value as a covariate. However, unlike longitudinal ANCOVA, the cLDA model accounts for variability in the baseline values, thus providing more accurate standard errors and CIs for individual treatment effects. Additional details pertaining to the use of the cLDA model in this trial are included in [Appendix 4](#).

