where $Y_{\bullet\bullet 0}$ is the mean response at baseline of all subjects in the analysis population. The default in the SAS MIXED procedure is to calculate the baseline mean from the analysis dataset. When data are missing, some subjects have fewer observations in the analysis dataset. As a result, the default baseline mean is a weighted average of baseline values across subjects, where the weight is proportional to the number of observations in the analysis dataset for a given subject. Under MAR, the weighted baseline mean may be biased.

To fix this problem, the baseline mean should be calculated outside of the SAS MIXED procedure, using one baseline observation per subject. This calculated mean can be used in the LSMEAN statement with the AT =option or in the ESTIMATE statement.

When the model is more complicated (adjustment for other factors), the ESTIMATE statement provides more flexibility.

6. Stratification

Adjustments for stratification factors (such as study center, gender, etc.) do not pose any additional theoretical difficulties, although assumptions between models that appear similar can be different. For example, adding a stratification and stratification by time interaction to the Longitudinal ANCOVA model defined in Section 2.1 implicitly makes several assumptions, including that (1) the correlation between baseline and post-baseline measurements is the same for each level of the stratification variable; and (2) the baseline means are the same for each level of the stratification factor. The LSMEAN estimates are calculated in SAS using this common mean. In contrast, an LDA model with the additional stratification and stratification by time factors does not impose the same implicit assumptions. As a result, estimates from the two models will not be the same, even when there are no missing data. An LDA model can be constructed that imposes the same implicit assumptions as the Longitudinal ANCOVA model when adjusting for additional stratification factors, although in most situations the less restrictive assumptions of the LDA model may make more sense.

7. REML and Kenward-Roger adjustment

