9.2 Adjusting for stratification variables when fitting the LDA model in SAS

An LDA model that adjusts for stratification variables can be fit within SAS using the following code (assuming equal weights for combining estimates across strata):

```
*****
**
** data step necessary prior to running SAS PROC MIXED;
*****
**
DATA long; SET long;
  ARRAY T{4} t0-t3; * time indicator variables;
  ARRAY TT{4} tt0-tt3; * time by treatment 1 (vaccine) indicator variables;
  ** define week times treatment 1 indicator variables;
  DO i = 1 TO 4;
    t{i} = (time=(i-1));
    tt{i} = t{i}*(trt=1);
  END;
  DROP i;
RUN;

*****
**
** LDA model fit in SAS PROC MIXED;
*****
**
PROC MIXED DATA=long;
  CLASS subj time strata;
  MODEL y=strata time strata*time tt1 tt2 tt3/ddfm=KR;
  REPEATED time / SUBJECT=subj TYPE=UN;
  ESTIMATE 'T1 Diff (V-P)' tt1 1;
  ESTIMATE 'T2 Diff (V-P)' tt2 1;
  ESTIMATE 'T3 Diff (V-P)' tt3 1;
  ESTIMATE 'T1 Placebo LSM' time -3 3 0 0
    strata*time -1 -1 -1 1 1 1 0 0 0 0 0 / divisor = 3;
  ESTIMATE 'T2 Placebo LSM' time -3 0 3 0
    strata*time -1 -1 -1 0 0 0 1 1 1 0 0 0 / divisor = 3;
  ESTIMATE 'T3 Placebo LSM' time -3 0 0 3
    strata*time -1 -1 -1 0 0 0 0 0 1 1 1 / divisor = 3;
  ESTIMATE 'T1 Vaccine LSM' time -3 3 0 0 tt1 3
    strata*time -1 -1 -1 1 1 1 0 0 0 0 0 / divisor = 3;
  ESTIMATE 'T2 Vaccine LSM' time -3 0 3 0 tt2 3
    strata*time -1 -1 -1 0 0 0 1 1 1 0 0 0 / divisor = 3;
  ESTIMATE 'T3 Vaccine LSM' time -3 0 0 3 tt3 3
    strata*time -1 -1 -1 0 0 0 0 0 1 1 1 / divisor = 3;
  ODS OUTPUT Estimates=outm1;
RUN;
```

Note that this model does not implicitly assume that the baseline means or the correlation between the baseline and post-baseline measurements are the same for each stratum. The typical Longitudinal ANCOVA model that does make this implicit assumption is fit within SAS using the following code:

```
*****
**
** Longitudinal ANCOVA model fit in SAS PROC MIXED;
*****
**
PROC SQL NOPRINT;
  SELECT mean(y) INTO: bb
  FROM long WHERE time=0;
QUIT;
PROC MIXED DATA=long;
  WHERE time>0;
  CLASS subj time trt strata;
  MODEL cy = bl trt time trt*time bl*time strata strata*time/ddfm=KR;
  REPEATED time / SUBJECT=subj TYPE=UN;
  LSMEANS trt trt*time / pdiff at bl=&bb;
  ODS OUTPUT LSMeans=outm2a Diffs=outm2b;
RUN;
```

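### The supportive cLDA model has no covariate-by-time terms, so its covariates cancel from mean change and the equality with longitudinal ANCOVA claimed in 8.2.1 does not hold for it (minor)

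*Combined protocol and SAP*

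**What the plan says.** **Primary model (8.2.1, Table 5).** "A longitudinal ANCOVA model will be used on the change scores". The covariates in 8.2.1 are region, gender, APOE genotype, baseline Vitamin E use, baseline AD medication and cohort, and the categorical list closes with "study cohort from the initial 78-week trial (Safety Cohort, Main Cohort) and the interaction of time-by-treatment". Two continuous covariates are added, MMSE and age at baseline. On the baseline score itself, the section says: "The baseline value of the dependent variable, as well as the baseline-by-time interaction term will also be included". The only interactions named are time-by-treatment and baseline-by-time.

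**Supportive cLDA on MFAS (8.2.1).** Baseline moves into the response vector, and the model is fitted "with all of the same covariates that were included in the primary model (now excluding the terms for baseline and baseline-by-time interaction".

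**Equality statement (8.2.1, next paragraph).** If no data are missing, "the estimated treatment difference from the above cLDA model will be identical to that from a traditional longitudinal analysis of covariance (ANCOVA) model" with baseline as covariate.

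**Appendix 4.** The introduction of the attached guidance limits the equality of point estimates to simple models that adjust for categorical time. Its section 9.2 code for a covariate-adjusted cLDA reads "MODEL y=strata time strata*time tt1 tt2 tt3/ddfm=KR". The section 10 template tells teams to consider time-by-factor terms.

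**The concern.** Carrying the same covariates into both models looks like keeping the adjustment constant, but the response differs. In the primary model it is change, so a covariate main effect adjusts change. In the cLDA it is the score itself, baseline included, so the same main effect adjusts level.

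Two things follow. The cLDA loses whatever precision the covariates would give for change. And a gap between the cLDA and primary results would reflect a changed covariate model as well as the intended change of method and population. A reader who trusts the equality sentence would put the whole gap down to missing data.

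**Working it through.** **Inputs**
- Model terms: 8.2.1 and Table 5.
- ADAS-Cog (Table 6): baseline SD 7.75, Week 104 SD 14.97, correlation 0.65.
- Numbers (Table 7 footnote): 570 per arm, 45% dropout at Week 104, so 570 × 0.55 = 313.5, about 314 per arm.
- Not in the documents, so assumed: covariate effects and R², and SDs and correlations at intermediate visits.

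**Step 1. Algebra.** For arm j and covariates X, the cLDA as written has E(Y_t | X) = γ0 + γ_jt + Xβ at every visit, with γ_j0 = 0. Hence E(Y_t − Y_0 | X) = γ_jt, and X cancels.

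Conditioning on baseline, with one follow-up visit T for simplicity:

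E(Y_T − Y_0 | Y_0, X) = γ_jT + (b − 1)(Y_0 − γ0) + (1 − b)Xβ, where b = ρ × SD_T / SD_0.

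Table 6 gives b = 0.65 × 14.97 / 7.75 = 1.256, so 1 − b = −0.256. The covariates still enter, but their coefficient is tied to β, their effect on level. The primary ANCOVA has E(Y_T − Y_0 | Y_0, X) = θ_jT + α_T Y_0 + Xδ, with δ free.

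**Step 2. Testing the equality.** Complete data were simulated for 570 per arm with baseline and four visits, Table 6 values and a true Week 104 difference of −2. One continuous and two binary covariates were given effects on level (−4, 1, 1) and on Week 104 change (−3, 3, 2). Both models were fitted by ML with unstructured covariance. One data set gives:

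| Covariate terms | cLDA | Longitudinal ANCOVA |
|---|---|---|
| None | −1.505361 | −1.505361 |
| Main effects only (8.2.1 as written) | −1.537645 (SE 0.7245) | −1.547688 (SE 0.7107) |
| Crossed with time in both | −1.719540 | −1.719540 |

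The plan's equality reproduces without covariates, fails for the model specified, and returns once covariate-by-time terms are in both models. The main-effects cLDA also differs from an ANCOVA with baseline as the only covariate (−1.537645 against −1.505361). With covariates unrelated to change, the main-effects estimates still differ: −2.191481 against −2.195289.

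**Step 3. Size.** The Week 104 residual SD given baseline is 14.97 × √(1 − 0.65²) = 11.38. At 314 per arm the SE is 11.38 × √(2/314) = 0.91. If the covariates explain a share R² of that variance, a model that adjusts change for them gains a factor of about √(1 − R²). The unadjusted SE is then larger by 1/√(1 − R²) − 1: 1.0% at R² = 2%, 2.6% at 5%, 8.5% at 15%.

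Simulation with complete data at 314 per arm gives slightly less:

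| R² (assumed) | cLDA SE above primary ANCOVA SE |
|---|---|
| 0–2% | about 0–1% |
| 5% | about 2% |
| 15% | about 7–8% |

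Across these settings the two estimates differ on the same data by an SD of about 0.04–0.27 points, with a mean difference of about zero. The upper end is 0.27/0.91, or about 0.3 of a standard error. Under the Step 2 type of assumptions at 313 per arm, the SD of the difference was 0.06–0.15 (largest 0.40). With the strong covariate effects the SEs were 0.947 and 0.922, a 2.7% excess.

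**The case against.** **The main-effects reading is inferred.** Section 8.2.1 never says main effects only, and it refers to Appendix 4, whose stratified code carries `strata*time`. This stands in part: the sponsor may have intended that form. But the primary model lists no such terms, the cLDA takes its covariates from that list, the template only asks teams to consider the interaction, and Section 8.0 says no separate SAP will follow. The literal text yields the main-effects model.

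**Appendix 4 might be read as conceding the point outright.** Section 6 of the guidance says that "estimates from the two models will not be the same, even when there are no missing data". A reader might infer that the sponsor itself declares this cLDA unequal to ANCOVA. The documents do not support that. The sentence concerns two models that both carry stratification-by-time terms, and its argument is about baseline means and LSMEANs. In Step 2 the treatment differences agree exactly in that case. The sound support is the guidance's introduction and its section 9.2 code.

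**The covariates are not ignored.** A reader might infer that they drop out altogether. They do not: they act through (1 − b)β. What is missing is a free effect on change.

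**Model and population change together by design.** This is correct. The analysis was never meant to isolate the MFAS effect, so the complaint is only that an unannounced third change is added.

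**The consequence is small.** This also stands. There are no formal hypotheses, the analysis is supportive, a slightly larger SE is conservative, and the equality sentence is conditional on complete data, which 45% assumed dropout rules out.

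**Conclusion.** The specification mismatch and the false equality statement hold on the text of 8.2.1. They follow from the model structure and need no numerical assumption. The severity is minor.

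The size does rest on assumptions. It runs from nothing to a 7–8% larger SE as the assumed R² goes from 0 to 15%, and the documents give no basis for choosing within that range. It might be inferred that the cLDA result is biased or materially weakened. Neither is supported: with complete data the mean difference between the models is about zero, and differences on the same data are small against an SE of about 0.91. The figures are for ADAS-Cog with complete data; ADCS-ADL and the effect of dropout were not simulated.

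**What to change.** In 8.2.1, state that each covariate in the cLDA sensitivity model is crossed with time, as in the stratified code in section 9.2 of the Appendix 4 guidance. Restrict the equality sentence to models without other covariates, or to the case where both models carry covariate-by-time terms.

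Unless the primary ANCOVA also gains these terms, the two estimates will agree closely but not exactly. With the terms in the cLDA alone, the simulated difference from the primary estimate had an SD of about 0.04–0.11 points at 314 per arm.

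The cost is one model line and one sentence. The 8.2.1 covariates use 10 degrees of freedom (region 3; gender, APOE, Vitamin E, AD medication, cohort, MMSE and age 1 each), so the change adds about 10 fixed-effect parameters per post-baseline visit. That is negligible with several hundred subjects per arm.

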8.2.2 Multiplicity

As there are no formal hypotheses for the long term safety trial, there is no need for a formal multiplicity strategy. However, 97.51% CIs will be produced for all endpoints with corresponding hypotheses conducted under strong control from the initial 78-week trial, even though formal hypotheses are not defined in this long-term safety trial, and it is acknowledged that strong control is not present.

8.2.3 Exploratory Analyses

It is noted that no supportive analyses (eg, to account for the effect of missing data or protocol violations) will be conducted for any of the exploratory analyses. Basic summary statistics will be provided (mean, standard deviation, quartiles, counts and percentages, as appropriate) by treatment, timepoint, and baseline AD severity (MMSE >20, MMSE ≤ 20) for all exploratory endpoints.

8.2.4 Subgroup Analyses

Subgroup analyses will be conducted on ADAS-Cog, ADCS-ADL, NPI, and MMSE at Week 104. The consistency of treatment effect across various subgroups will be assessed through the computation of within-group summary statistics (model-based and as-observed). Further, model-based between-group treatment differences and the corresponding 95% CIs will be constructed for those comparisons (active/active vs. placebo/active), for which both treatment groups within the subgroup level have at least 85 subjects (roughly 15% of subjects randomized). No formal statistical testing of the treatment-by-subgroup interactions will be performed. The following subgroups will be examined:

- Gender (male, female);
- Age (< trial median age, ≥ trial median age);
- Race (white, black, Asian, other);
- Randomization Cohort (Safety Cohort, Main Cohort)
- Ethnicity (Hispanic, Not Hispanic);
- Geographic Region (US/Canada, Europe/Australia/New Zealand, Japan, Rest of the World);
- APOE Genotype (APOE 4 positive, APOE 4 negative);
- Disease Severity via MMSE (mild AD: MMSE >20; moderate AD: MMSE ≤ 20);
- Trial Completion Status (Completer, Non-completer);
- AD Treatment at Screening (use of AChEI alone, use of memantine alone, use of AChEI and memantine, no use of AChEI or memantine);
- Vitamin E use at Screening (0-400 IU/day, > 400 IU/day)
- Behavioral Symptoms at Baseline (without symptoms NPI = 0, with symptoms NPI > 0);
- Total Hippocampal Volume (AD profile positive, AD profile negative);
- Evidence of Brain Amyloidosis in CSF and/or amyloid PET substudies (positive, negative);
- Highest Education Level (No Undergraduate Degree, Undergraduate Degree or Higher)

Regarding total hippocampal volume, an AD profile will be determined as described in the technical manual. The precise criteria to define an AD profile positive and AD profile negative subjects have not yet been determined but will be selected based on ongoing research at academic sites which is expected to be published before the end of this trial. Similarly, cutoffs for evidence of brain amyloidosis, as measured by CSF and PET, will also be defined based on ongoing studies. All cutoffs will be prespecified prior to the final database lock and will be documented in a memo-to-file.

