7.2 Beginning and End of the Trial

Each subject is considered to be enrolled when the subject (or the subject's legal representative) has provided written informed consent **in accordance with local requirements**.

This long term safety trial will start with enrollment of the first subject who completes the initial 78 week trial and will end when the drug either becomes commercially available or when the MK-8931 program is terminated. This long term safety trial has an expected maximum duration of approximately 260 weeks, with the duration of individual subject participation dependent on the timing of enrollment. Duration of participation may also be limited based on local regulations.

Each subject is considered to have ended participation in the trial when he/she has completed the last protocol-specified contact (eg, visits or telephone contacts) or has prematurely discontinued from the trial. A subject will be considered a completer of this long term safety trial if he/she is still continuing in the trial when the trial is stopped.

A subject is considered to have discontinued after he/she has withdrawn consent or has been discontinued under the conditions specified in **Section 7.3.3**. All applicable activities scheduled for the final trial visit should be performed at the time of treatment discontinuation as defined in the long term safety trial Flow Chart in **Section 2.2**.

A subject is considered to have been lost to follow-up if he/she is unable to be contacted by the investigator. The end of participation for a subject lost to follow-up is the last known contact (eg, visit or telephone contact).

Each subject will be monitored for the occurrence of AEs beginning immediately after the subject has signed informed consent through 14 days after cessation of treatment. Follow-up procedures related to pregnancy or existing SAEs may continue beyond the end of the clinical trial.

Given the exploratory nature of the extension trial endpoints, the retrieved dropout approach employed in the main cohort/safety cohort trial period (initial 78 week treatment period), will not be applicable to this extension trial period. Thus, subjects who discontinue study medication during the extension trial period will be discontinued from the study.

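### Section 8.2.4 uses trial completion status, a post-randomisation outcome, as a Week-104 treatment-effect subgroup, so those within-level contrasts are not protected by randomisation

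*Combined protocol and SAP*

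**What the plan says.** Section 8.2.4 sets the scope: "Subgroup analyses will be conducted on ADAS-Cog, ADCS-ADL, NPI, and MMSE at Week 104". Its purpose is to judge whether the treatment effect is consistent across subgroups. It plans within-group summaries throughout. It adds that "model-based between-group treatment differences and the corresponding 95% CIs will be constructed for those comparisons" of active/active with placebo/active in which "both treatment groups within the subgroup level have at least 85 subjects (roughly 15% of subjects randomized)". It also states: "No formal statistical testing of the treatment-by-subgroup interactions will be performed".

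Fifteen subgroup variables follow. Fourteen describe subjects at entry or at baseline (sex, age, region, APOE genotype, baseline severity and so on). The other is "Trial Completion Status (Completer, Non-completer)". The section neither defines it nor adds a caveat.

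The only definition of a completer for this trial is in section 7.2, which requires that "he/she is still continuing in the trial when the trial is stopped". The same section gives the extension an expected maximum of about 260 weeks and says that subjects who stop study medication in the extension leave the study. Section 8.2.1 keeps the data of subjects who never enter the extension. Section 8.2.7 says that dropout for lack of efficacy may depend on observed efficacy, and that treatment may largely determine dropout for other reasons, such as adverse experiences.

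**The concern.** A subgroup contrast keeps the protection of randomisation only if membership could not have been influenced by treatment or by the outcome. Completion status can be influenced by both. If decline or tolerability drives who stays, and either differs by arm, the completers in the two arms are selected differently, and so are the non-completers. A difference within a level then mixes the treatment effect with that selection, and its 95% CI does not reflect the selection.

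What is at stake is interpretation. The display is meant to show consistency of effect. A reader could take a gap between the two levels as effect modification, or take the completer result as the effect in people who stay on drug. The contrast identifies neither.

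**Working it through.** **1. The 85-subject rule.** Table 7 uses 570 per arm: 0.15 × 570 = 85.5, and 85/570 = 14.9%. The plan's rounded figure reproduces.

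**2. When status is settled.** Table 7 assumes 45% dropout by Week 104: 570 × 0.45 ≈ 256 per arm have left and 570 × 0.55 ≈ 313 remain. For the 256, non-completer status is fixed before Week 104. For the 313 it is fixed later, up to 338 − 104 = 234 weeks later on the section 2.2 schedule.

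**3. Whether the differences would be produced.** Section 8.2.4 does not say whether the 85 must have Week-104 data, or how subjects who never entered the extension are classed. I count the latter as non-completers.
- Non-completers: at least 256 per arm, about three times the threshold, if subjects without Week-104 data count. If a Week-104 score is required, the level can fail. At 45% completion, 570 × 0.45 ≈ 256 complete, leaving only 313 − 256 = 57 non-completers per arm seen at Week 104.
- Completers: the level passes if 85 of about 313 (27%) stay until the trial stops.

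**4. Illustrative size (ADAS-Cog).** The documents state no Week-104 effect, so one is back-solved from Table 7.
- Residual SD from Table 6: 14.97 × √(1 − 0.65²) = 11.38.
- With 313.5 per arm, two-sided α = 0.0249 and power 62.3%: (2.243 + 0.313) × 11.38 × √(2/313.5) = 2.32 points, or 31.2% of 7.45.

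Assume a true difference δ = 2.32 in every subject, and a latent retention score correlated −ρ with Week-104 change (higher change is worse). A subject completes if the score exceeds a common cut-off c. Put m = ρδ/SD, λ(x) = φ(x)/(1 − Φ(x)) and κ(x) = φ(x)/Φ(x). Then:
- completer difference = δ − ρ·SD·[λ(c) − λ(c − m)]
- non-completer difference = δ − ρ·SD·[κ(c − m) − κ(c)]

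Example with ρ = 0.5 and 30% completion: m = 0.5 × 2.32/11.38 = 0.102 and c ≈ 0.576. Then λ(c) ≈ 1.197 and λ(c − m) ≈ 1.122, so the completer difference is 2.32 − 5.69 × 0.075 ≈ 1.89.

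| ρ | Completion | Completers (shortfall) | Non-completers (shortfall) |
|---|---|---|---|
| 0.3 | 20% | 2.16 (7%) | 2.23 (4%) |
| 0.3 | 30% | 2.17 (7%) | 2.21 (5%) |
| 0.3 | 45% | 2.18 (6%) | 2.19 (6%) |
| 0.5 | 20% | 1.87 (20%) | 2.08 (10%) |
| 0.5 | 30% | 1.89 (18%) | 2.03 (13%) |
| 0.5 | 45% | 1.94 (17%) | 1.97 (15%) |

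Both levels are too small although no subgroup effect exists.

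**5. Direction is not fixed.** A separate simulation used a logistic completion model, 40% completers and SD 11.55 (differences are 40/40 minus placebo/40).
- True effect zero, completion depending on both outcome and treatment: completers/non-completers showed −0.63/−0.60 under moderate dependence and −2.02/−1.83 under strong dependence. They showed +1.54/−2.52 when the outcome dependence differed by arm.
- Completion unrelated to outcome: no bias.
- True effect zero and completion unrelated to treatment: no bias.

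None of these dependence strengths comes from the documents.

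**The case against.** The strongest reply is that little turns on this. It is one of fifteen descriptive subgroups with no interaction tests, in a trial without formal hypotheses, and dropout has its own tipping-point analysis. In the table above the shortfall is at most 0.45 points. The standard error of a completer difference is 11.38 × √(2/114) = 1.51 at 20% completion and 11.38 × √(2/256) = 1.01 at 45%. The two levels also shift together, differing by at most 2.08 − 1.87 = 0.21, so a consistency reading is barely disturbed. All of that stands for those scenarios, and it limits the severity. It does not carry over to the scenarios in which completion also depends on treatment.

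The illustration is also not the planned analysis. It gives every subject a Week-104 score and compares raw means, whereas the plan fits a longitudinal model that borrows from earlier visits. That stands too, so the figures show a mechanism and do not forecast a result. The model would supply the Week-104 information that many non-completers lack, which makes that level more dependent on its assumptions.

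A reader might suppose that completion here means the initial 78-week trial. Section 8.2.4 does not say so. Even then the status would be post-randomisation, and only the timing in step 2 would change.

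Three stronger readings are tempting and not supported. One is that status is always determined after Week 104: by the plan's own assumption it is fixed earlier for about 45% of each arm. Another is that a difference and CI will appear for each level regardless: the 85-subject condition applies. The third is that the two differences are demonstrably biased: that needs a dropout mechanism which section 8.2.7 anticipates but does not quantify.

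**Conclusion.** The point holds as a minor but real flaw. Completion status is the one listed subgroup that is an outcome of the trial. The plan expects that outcome to depend on efficacy and possibly on treatment, and no caveat is given. The within-level contrasts are therefore not randomised comparisons and are liable to bias whose size and direction the documents do not determine. The 4-20% shortfall rests on a back-solved effect of 2.32, assumed correlations of 0.3-0.5 and assumed completion of 20-45%. It would be nil if completion were unrelated to outcome. The primary Week-104 estimate does not use this subgroup and is unaffected.

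**What to change.** Delete Trial Completion Status from the treatment-effect subgroups in section 8.2.4. If a description of completers and non-completers is wanted, give observed summaries within each arm by completion status, using the section 7.2 definition. State how subjects who never entered the extension are classed, label the display as not a randomised comparison, and omit between-arm differences and CIs. Leave the effect of dropout to the tipping-point analysis in section 8.2.7. The cost is one descriptive table. Data collection and the primary analysis do not change.
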